## OBJECTIVES/ SPECIFIC AIMS/ HYPOTHESES

**A priori selected grey matter Regions of Interest for aim 1:** Based on our preliminary data and the summary of literature outlined in table 1, we propose the following *a priori* selected ROIs for the **cortical and deep grey matter and nuclei for aim 1**: Inferior frontal and precentral gyrus, thalamus, PAG, and pons. **A priori selected white matter tracts (WMT) for aim 2:** Since MS lesions affect the white matter mainly, it is prudent to evaluate the WMT involved in bladder function in this patient population. Two WMTs are particularly important in proper function of the bladder: Anterior thalamic radiation (ATR) and Superior longitudinal fasciculus (SLF).

Clinical and UDS data will be used to categorize female MS patients with stable disease into two groups. The standardization of terminology by the International Continence Society does not provide clear definition for VD, however we propose the following based on expert opinion. Group 1: MS patients with VD (patients who perform self-catheterization or have a postvoid residual of urine  $\geq 20\%$  Maximum Cystometric Capacity); and Group 2: MS patients without VD (patients who void spontaneously and their postvoid residual of urine  $< 40\%$  Maximum Cystometric Capacity). Patients in Group 1 will be further subdivided into patients with DSD (Group 1a) versus without DSD (Group 1b). DSD is defined as increased EMG activity  $\geq 20\%$  during detrusor contraction (voiding) in the absence of valsalva maneuvers on UDS.

We **hypothesize** that female MS patients with VD have a distinct pattern of brain activation and connectivity at “initiation of voiding” and targeted cortical modulation may be feasible and lead to improved voiding.

**Specific Aim 1: Activation patterns of the grey matter ROIs are different among female MS subjects with VD, specifically those with DSD.** We will determine the distinct activation patterns by:

- Assessing Blood Oxygen Level Dependent (BOLD) signal and functional connectivity (FC) patterns in the ROI's at “initiation of voiding” in Groups 1a, 1b, and 2.
- Comparing BOLD signals and FC patterns in Group 1 versus 2, and specifically Group 1a versus 1b.

**Specific Aim 2: Damage to preselected WMT in female MS patients provides an independent predictive measure for VD.** We will use diffusion tensor imaging and our established algorithm of measurement to:

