### Secondary Endpoints

- a) FA and MD of ATR and SLF white matter tracts in Groups 1 and 2.
- b) Clinical scores: UDS parameters, urinary symptom scores, surveys at baseline and following TRPMS.
- c) BOLD signal characteristics and FC patterns in ROIs in patients with versus without DSD.

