## Selection and Recruitment of the Subject

**Inclusions:** Adult female patients with clinically stable MS [Expanded Disability Status Score (EDSS)  $\leq 6.5$ ], with bladder symptoms  $\geq 3$  months, will be screened. Patients will be considered to have VD if they have an increased Postvoid Residual ( $\geq 20\%$  Maximum Cystometric Capacity) or abnormally slow and /or incomplete micturition based on abnormally slow urine flow rates. Patients who perform self-catheterization will be included in the VD category as well.

Patients with active UTI can be treated and subsequently screened for the trial.

**Regarding patients with DSD:** Appropriately placed and traced perineal surface electrodes used for EMG recordings can be used to determine presence or absence of DSD. There is no clear cutoff or consensus for the amount of EMG activity change during the voiding phase. We will use increased EMG activity by 20% during detrusor contraction (voiding), in the absence of valsalva maneuvers, to determine DSD.

**Exclusions:** Men, anatomical bladder outlet obstruction (anti-incontinence procedures, urethral strictures, or advanced pelvic organ prolapse). Severe debilitating MS, history of seizures, pregnancy or planning to become pregnant, contraindications to MRI, history of augmentation cystoplasty, presence of other neurological disorders besides MS.

**Relevant biological variables (sex):** At this point, males are excluded from our evaluation to avoid potential confounding factors by common bladder outlet pathologies secondary to benign or malignant prostatic pathology, primary bladder neck obstruction, and urethral strictures (all common in men). In addition posture during urination (lying flat in the scanner versus sitting or standing) appears to affect voiding and this difference is more noticeable in males versus females, especially when bladder symptoms are present. Due to these differences between sexes and the possibility of them being confounding factors at this point we are excluding males.

**Subject recruitment:** Our Neurourology Clinic where I serve as the clinical director, has three fulltime fellowship trained urologists and is a referral center in Houston. My mentor and chairman [name] is a nationally recognized clinician in this field. Eligible patients for our study will be screened and recruited from our clinic.

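### The definitions of Group 1 (voiding dysfunction) and Group 2 (no voiding dysfunction) overlap, so the main group comparison is not uniquely defined

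*Combined protocol and SAP*

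**What the plan says.** The section Objectives/Specific Aims/Hypotheses sorts female MS patients into two groups using clinical and urodynamic data. It notes the lack of a clear standard definition of VD and continues, "however we propose the following based on expert opinion". Group 1, with VD, is "patients who perform self-catheterization or have a postvoid residual of urine $\geq 20\%$ Maximum Cystometric Capacity". Group 2, without VD, is "patients who void spontaneously and their postvoid residual of urine $< 40\%$ Maximum Cystometric Capacity".

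The inclusion criteria under Selection and Recruitment of the Subject define VD again: "Patients will be considered to have VD if they have an increased Postvoid Residual ( $\geq 20\%$ Maximum Cystometric Capacity) or abnormally slow" or incomplete micturition judged from slow flow rates. They add: "Patients who perform self-catheterization will be included in the VD category as well".

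The labels are then used in three places:

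- Aim 1: "Comparing BOLD signals and FC patterns in Group 1 versus 2, and specifically Group 1a versus 1b".
- Aim 2 and the first secondary endpoint: "FA and MD of ATR and SLF white matter tracts in Groups 1 and 2", with tract damage examined as a predictor of VD.
- Aim 3: Group 1 is the stimulated population, and its activation pattern is judged against Group 2 or healthy controls.

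The Power Analysis paragraph plans 13 patients per group (26 in total) and says that recruitment and scanning for Aims 1 and 2 are finished.

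**The concern.** Two groups that are to be compared must be mutually exclusive. Here the lower bound for Group 1 (20% of maximum cystometric capacity) lies below the upper bound for Group 2 (40%), and no order of precedence is given. Two analysts who follow the text faithfully could build different groups from the same records.

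Two things are at stake. First, if patients with VD are placed in Group 2, the contrast is diluted, and with 13 per group a few patients matter. Second, Aims 1 and 2 are retrospective analyses of data already in hand. The Preliminary Data section already reports activation at initiation of voiding in MS patients, including a subgroup of four with detrusor sphincter dyssynergia (DSD). With the rule open, the allocation could be settled after the imaging results are known.

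**Working it through.** **1. Apply the two definitions.** Take residual as a percentage of maximum cystometric capacity, and treat self-catheterization as not voiding spontaneously.

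| Patient | Group 1 (catheterizes, or residual ≥20%) | Group 2 (spontaneous, and residual <40%) |
|---|---|---|
| Spontaneous, residual <20% | no | yes |
| Spontaneous, residual 20% to <40% | **yes** | **yes** |
| Spontaneous, residual ≥40% | yes | no |
| Self-catheterizing, any residual | yes | no |

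The overlap is the interval from 20% up to but not including 40%, which is 40 − 20 = 20 percentage points wide.

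**2. Compare with the inclusion criteria.** These add a further route to VD: "or abnormally slow and /or incomplete micturition based on abnormally slow urine flow rates". A spontaneous voider with slow flow and a residual below 20% has VD there, but meets only Group 2 in the aims section. This conflict is separate from the first.

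**3. The plan's own sample size.** The Power Analysis starts from about 12 subjects and allows 10% exclusions: 12 × 1.10 = 13.2, or 13 per group and 26 in total. (Dividing instead, 12/0.90 = 13.3, gives 14 when rounded up.) The stated figure is reproduced closely and does not depend on the overlap. No effect size, standard deviation or alpha is given, so the power figures below need an assumed effect.

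**4. Dilution (illustration).** Assumptions: one two-sample t-test, two-sided 5%, 13 v 13, and a standardized difference d = 1.145, which gives 80% power. Suppose m of the 13 Group 2 patients carry the full Group 1 pattern. The expected difference becomes d × (1 − m/13), and power follows from the noncentral t distribution with 24 degrees of freedom.

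| m | 1 − m/13 | Shrinkage | Diluted d | Power |
|---|---|---|---|---|
| 0 | 1.000 | 0% | 1.145 | 80.0% |
| 2 | 0.846 | 15% | 0.969 | 65.9% |
| 3 | 0.769 | 23% | 0.881 | 57.7% |
| 4 | 0.692 | 31% | 0.793 | 49.2% |

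This formula leaves the variance unchanged. Simulating the mixed group directly, so that its extra variance counts, gives about 63%, 53% and 44%.

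**5. Choosing the allocation after the results (illustration).** Simulate 26 patients with no true difference: 11 fixed in each group and 4 ambiguous. Reject if the smallest p-value over the permitted allocations is below 0.05.

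- Two blanket rules (all four to Group 1, or all four to Group 2): type I error about 8%.
- Any of the 2⁴ = 16 individual allocations: about 16% to 17%.

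**6. What a consistent rule costs in power.** If the ambiguous patients had been in Group 2 and all move to Group 1, the split goes from 13/13 to 15/11, 16/10 or 17/9. At the same d, power is about 79%, 78% or 76%. Unequal groups cost much less than misplaced patients.

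**The case against.** The best defence reads the two sections together. Group 2 is labelled as being without VD, and the inclusion criteria call a residual of 20% or more VD, so the disputed patient would belong to Group 1. On this reading, 40% is one inconsistent number, since it appears once and 20% twice. That is plausible, but it contradicts the written upper limit for Group 2 and so does not resolve it. A slip would still have to be corrected.

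Other points stand in part:

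- **The band may be empty.** The documents give no count. The two to four patients used above are assumed, as is d.
- **The model is simplified.** The plan uses voxel-level group tests and FDR-corrected connectivity, not one t-test. A patient in the band may also have only an intermediate pattern, which would dilute the contrast less.
- **Not everything depends on the labels.** The primary endpoints as listed name no group contrast, and the one on change after stimulation is within-patient. The DSD subgroups are affected only through who enters Group 1. Aim 3 is a pilot of eight patients and can also use healthy controls as its reference.
- **Grouping is meant to use clinical and urodynamic data.** This makes patient-by-patient choice on imaging unlikely, so the 8% figure is more realistic than the 16% to 17%. But no date for fixing the groups is given.

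These points limit the consequence. They do not remove the overlap.

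**Conclusion.** The concern holds. Every spontaneous voider with a residual from 20% to below 40% of capacity meets both group definitions, and a slow-flow patient below 20% is classified differently in two sections. This follows from the text alone, without assumptions. It leaves the Aim 1 contrast, the Aim 2 outcome and entry to the Aim 3 population without a unique definition.

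The practical size cannot be read from the documents. Under the stated assumptions, two to four misplaced patients would take power from 80% to between about 66% and 49%, and a choice between two blanket rules after seeing the data would raise a 5% error rate to about 8%. The correction should be made before any group analysis is run.

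**What to change.** - **One rule, stated identically in both sections.** Make Group 2 the exact complement of Group 1. For example, if the VD cut-off that both sections already state is kept, Group 2 becomes patients who void spontaneously, do not catheterize and have a residual below that same value. The documents cannot show which number was intended. Because Group 1 membership also governs entry to Aim 3, the sponsor must decide and give the reason.
- **Slow flow.** State in both sections whether slow flow with a low residual counts as VD and, if it does, the criterion for it.
- **Freeze the list.** Fix and date each patient's group from clinical and urodynamic data before any imaging contrast is run. Report how many patients fall in the 20% to <40% band.
- **One sensitivity analysis.** Repeat the Group 1 v Group 2 comparison without the patients in that band.

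The cost is protocol and SAP wording plus relabelling of existing records, with no new data. The groups may no longer be 13 and 13, and the Power Analysis paragraph should then give the actual split.

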### 3. APPROACH

#### Preliminary Data over the past four years

[figure not shown]
a three-dimensional augmented reality (AR) device in HC during repetitive voiding. The network under investigation was found to consist of two large sub-networks, one in the frontal lobe and one that connected sensory regions with deeper brain structures, including the PMC. This data will serve as our HC for this proposal.

**MS patients:** We have evaluated twenty-seven MS patients with neurogenic lower urinary tract dysfunction using our established fMRI/UDS platform. Our analyses described, for the first time, brain regions activated at initiation of voiding in female

Figure 4. BOLD signals at initiation of voiding. A, HCs B, MS showing higher signals in regions with warmer colors. C, subtraction image between MS and HCs.

**Healthy Controls (HC):** Our established fMRI/UDS platform demonstrated activation of brain regions of cerebellum, thalamus, caudate, lentiform nucleus, supplementary motor area, postcentral gyrus, left superior frontal gyrus, anterior and posterior cingulate gyrus and insula, as well as other brain structures such as the pons at the time of “initiation of voiding” HC, figure 3. We also have established an algorithm visualization and evaluation of neuroimaging data

Figure 3. Average fMRI activation maps with concurrent UDS tracings. Asterisk denote “initiation of voiding” in the event-related analysis of the fMRI data in HC.

[figure not shown]

MS patients (Figure 4).

**MS patients with DSD:** Our data on a subgroup analysis of MS patients with DSD (n=4), showed statistically significant greater activation in the right middle frontal gyrus, right medial frontal gyrus, right cingulate gyrus, right caudate nucleus, and brainstem at “initiation of voiding”.

**Changes in brain following intradetrusor injection of OnabotulinumtoxinA (IDBTX-A):** fMRI/UDS results from our recent study examining the impact of IDBTX-A in MS with urinary urgency (N=12) demonstrated that activation increased in specific brain regions associated with the sensation and process of urinary urgency six weeks post therapy (Figure 5). This is the first study of its kind to evaluate the possible sensory effects of IDBTX-A in humans. These preliminary results have been submitted to the 2018 national Urology and Neurology meeting.

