- Measure fractional anisotropy (FA) and mean diffusivity (MD) of the ATR and SLF in Groups 1a, 1b, and 2.
- Assess whether damage to SLF or ATR are associated with voiding dysfunction in our patient population.

**Specific Aim 3: Targeted cortical stimulation in Group 1 causes changes in ROI (identified during specific aim1) that better recapitulate the activation patterns in group 2 or HCs by:**

- Assessing BOLD and FC activation in the ROIs following individualized TRPMS in patients in Group 1.
- Evaluating voiding improvement via UDS and validated questionnaires following TRPMS.

- c) Identifying baseline clinical/UDS or neuroimaging factors that could predict response to TRPMS.
- d) Evaluating EMG changes in the pelvic floor following TRPMS.

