## Data Collection and Statistical Analysis

Three-dimensional structural images are obtained from a T1-weighted sequence; (sagittal direction, 0.7 in-plane resolution) as well as functional images collected with simultaneous UDS (axial echo-planar, TR = 3,000ms, 4.0mm slice thickness, 3.38mm in-plane resolution). AFNI software will be used for analysis. Structural and functional images will be registered and motion-corrected. Patients with rapid motion (> 4.5mm) will be excluded from analysis. Voxel activation will be identified at “initiation of voiding” which is signaled by patient’s right hand. Significant differentially-activated voxels will be identified under the generalized linear model. Group level analysis will be performed by transforming data into Talairach space, and significantly activated/deactivated voxels will be identified using a Student’s T-test or a non-parametric test if indicated. We will use SPSS (v19.0) to perform statistical analysis of clinical data (i.e. demographic, UDS data). FC analysis will be performed using CONN, a functional connectivity toolbox for MATLAB, Version 15a, which utilizes the statistical parametric mapping MATLAB toolbox. fMRI images acquired during the voiding task together with their corresponding anatomical datasets will be processed using the default- Montreal Neurological Institute (MNI) preprocessing option to enable group analysis in MNI space. A region-based connectivity analysis will be performed for each patient group based on ROIs. FC will be quantified by T-values for a p-value < 0.05 (two-sided, FDR-corrected). Diffusion Tensor Imaging (DTI) images will be acquired (32 directions, one B0 image) using the standard MRI pulse sequence available on the Siemens 3Tesla or 7 Tesla MRI scanner. The software packages TackVis (version 0.6.0.1) and the Diffusion Toolkit (version 0.6.3, trackvis.org) will be used to calculate and extract selected white matter tracts of interest. This software also enables calculating FA and MD values for the segmented WMTs.

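### Aim 1 claims a DSD-specific activation pattern but plans no test of either VD subgroup against Group 2, so a 1a v 1b difference cannot be attributed to DSD

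*Combined protocol and SAP*

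**What the plan says.** The Objectives section splits the VD group: "Patients in Group 1 will be further subdivided into patients with DSD (Group 1a) versus without DSD (Group 1b". The hypothesis of Specific Aim 1 is "Activation patterns of the grey matter ROIs are different among female MS subjects with VD, specifically those with DSD".

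Two bullets follow. The first is descriptive and covers Groups 1a, 1b and 2 separately: "Assessing Blood Oxygen Level Dependent (BOLD) signal and functional connectivity (FC) patterns in the ROI's at" initiation of voiding. The second names the contrasts: "Comparing BOLD signals and FC patterns in Group 1 versus 2, and specifically Group 1a versus 1b". The primary and secondary endpoints and the Data Collection and Statistical Analysis section name no test of 1a or 1b against Group 2. The analysis section offers a t-test "or a non-parametric test if indicated" for group-level activation, and a connectivity analysis within each patient group.

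Two other places bear on this. Specific Aim 3 says that stimulation "causes changes in ROI (identified during specific aim1) that better recapitulate the activation patterns in group 2 or HCs", so Group 2 is one of its two reference patterns. Secondary endpoint (c) is "BOLD signal characteristics and FC patterns in ROIs in patients with versus without DSD", and does not say whether the patients without DSD are 1b alone or 1b plus Group 2.

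The Power Analysis gives 13 patients in each of Groups 1 and 2. It gives no size for 1a or 1b.

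**The concern.** A claim that a region behaves abnormally in DSD needs two things: 1a differs from other VD patients, and 1a differs from patients who void normally. The plan tests the first only. A significant 1a v 1b result fits an abnormal 1a with a normal 1b, the reverse, or smaller deviations in both. The pooled 1 v 2 test does not reliably settle which, because in it each subgroup counts only for its share of Group 1.

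At stake is what Aim 1 may report. Since the hypothesis singles out DSD, a positive 1a v 1b contrast is likely to be written up as a DSD finding, even where the non-DSD patients are the ones who differ from Group 2. Such a region could then enter the set of regions examined in Aim 3.

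**Working it through.** **Inputs from the documents.** About 12 subjects for 80% power at single-voxel level, 10% exclusions, 13 per group and N = 26 (Power Analysis). Two-sided 0.05, FDR-corrected, for connectivity (Data Collection and Statistical Analysis); no threshold is stated for BOLD. The only DSD count is in the preliminary data, a "subgroup analysis of MS patients with DSD (n=4"), which is not stated to be the Aim 1 subgroup size.

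**Assumptions.** Normal data, SD 1, two-sided 5% without correction, n(1a) from 4 to 9 of 13, and shifts of 1.2 or 1.5 SD. The 1.2 is an anchor: 12 v 12 with a t-test has 80% power at a difference of 1.20 SD. Rejection rates are from simulation.

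**The plan's own figure.** 12 × 1.1 = 13.2 and 12 / 0.9 = 13.3. Both round to 13 (14 if rounded up), so 13 per group and 26 in total are reproduced within rounding. The base figure of 12 cannot be derived, because no effect size or SD is given.

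**Step 1: dilution in 1 v 2.** If only 1a is shifted, by d, the expected 1-2 difference is d × n(1a)/13. Results at d = 1.2:

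| n(1a) | Expected 1-2 difference | Power 1 v 2 | Power 1a v 1b | Power 1a v 2 |
|---|---|---|---|---|
| 4 | 1.2 × 4/13 = 0.37 | 11% | 45% | 50% |
| 6 | 1.2 × 6/13 = 0.55 | 21% | 50% | 62% |
| 9 | 1.2 × 9/13 = 0.83 | 47% | 44% | 75% |

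The pooled test is weak when few patients have DSD, but the planned 1a v 1b test sees the full shift.

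**Step 2: what 1a v 1b can distinguish.** Write the true deviations from Group 2 as (1a, 1b). The truths (+1.2, 0), (0, -1.2) and (+0.6, -0.6) all give 1a-1b = 1.2. With 4 and 9 patients, the expected 1-2 differences are:
- (4 × 1.2 + 9 × 0)/13 = +0.37
- (4 × 0 - 9 × 1.2)/13 = -0.83
- (4 × 0.6 - 9 × 0.6)/13 = -0.23

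So the two planned contrasts together carry the information as estimates: 1a-2 = (1-2) + [n(1b)/n(1)] × (1a-1b). For the first truth this is 0.37 + (9/13) × 1.2 = 1.20. No test of that quantity is planned. The two planned tests are also seldom positive together: with only 1a shifted, by 1.5 SD, both reject in about 8% of runs at n(1a) = 4 and 19% at n(1a) = 6.

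**Step 3: false attribution.** Now let only 1b be shifted, by 1.2 SD, with 1a equal to Group 2. The rejection rate of 1a v 1b depends only on the size of the difference and the two subgroup sizes, so it is again about 45 to 50% over n(1a) = 4 to 9. At 4/9/13, 1a v 2 rejects in 5% of runs (its null is true) and 1b v 2 in about 75%. Requiring 1a to differ from both 1b and Group 2 cannot succeed more often than 1a v 2 alone, which is 5%. Simulated, the joint event occurs in about 3%.

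**Step 4: price of the joint rule.** At 4/9/13 with only 1a shifted by 1.5 SD, 1a v 1b alone has about 62% power. The joint rule in a three-group model has about 58%, before multiplicity control.

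**The case against.** The strongest reply is that Aim 1 already catches a DSD-only effect, because 1a v 1b is undiluted. This stands. At 4/9/13 and 1.5 SD, a reader might set 14% power for 1 v 2 beside 71% for 1a v 2 in a three-group model and infer a large loss. That comparison ignores the planned 1a v 1b test at about 62%. With alpha split over two added contrasts, 1a v 2 falls to about 59%, so there is no power gain in that setting.

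A reader might also infer that pooling could cancel a DSD-only effect. It cannot: d × n(1a)/13 keeps the sign of d. Cancellation requires 1b to deviate in the opposite direction, and then 1a v 1b is the more powerful for it. With 6 and 7 patients at +1.2 and -1.03, 1 v 2 rejects in about 1% of runs and 1a v 1b in 95%.

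Nor is the direction hidden. Patterns are to be described in 1a, 1b and 2 separately, and connectivity is run for each patient group. This narrows the point to a missing test but does not remove it: with perhaps four patients in 1a, judging by eye which subgroup departs from Group 2 gives no error control.

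Finally, a reader might infer that Aim 3 loses its basis. The documents do not support that. Its reference may also be healthy controls, the Aim 1 and 2 regions are added to those in Table 1, targets are individualised, and Aim 3 is a pilot of 8.

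**Conclusion.** The point holds as one of attribution. The plan states a DSD-specific hypothesis and names no test that could establish it against Group 2. If the abnormality lies in the non-DSD patients, the planned 1a v 1b contrast is positive in about 45 to 50% of runs and could be read as a DSD finding; requiring a second difference from Group 2 reduces that to about 3%.

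These figures rest on an assumed 1.2 SD shift, unit SD, n(1a) of 4 to 9 of 13, and uncorrected tests. That no 1a v 2 or 1b v 2 test is named can be read from the text and needs no assumption. The documents do not support saying that Aim 1 would miss a DSD effect.

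**What to change.** 1. **Reconcile the groups first.** The Objectives section admits patients to Group 1 with a postvoid residual of at least 20% of maximum cystometric capacity, and spontaneous voiders to Group 2 with a residual below 40%. A spontaneous voider at 20% to under 40% fits both. No contrast with Group 2 is interpretable until these definitions are reconciled.
2. **Model.** In Aim 1 and in Data Collection and Statistical Analysis, fit one three-group model (1a, 1b, 2) with a common error term for each region's BOLD signal and for each region-pair connectivity.
3. **Contrasts.** Keep 1-2 and 1a-1b, add 1a-2 and 1b-2, and control multiplicity over all four, not just the two added. As a rough guide, four unadjusted 5% tests give 1 - 0.95^4 = 18.5% if independent, which these are not.
4. **Rule.** Call a region DSD-specific only if 1a differs from both 1b and Group 2.
5. **Wording.** State that the comparator in secondary endpoint (c) is 1b, and give the sizes of 1a and 1b.

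**Cost.** The Power Analysis section says that recruitment and scanning for Aims 1 and 2 are complete and analysis is pending, so this changes analysis text only. The price is more contrasts and somewhat lower sensitivity than 1a v 1b alone, with a further loss once multiplicity is controlled.

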## EXPERIMENTAL PLAN AND FEASIBILITY

We have completed and recently published a well-powered study, on twenty-seven female MS patients, that evaluated brain response to bladder filling during the bladder *storage phase*. Aims 1 and 2 are retrospective analysis of the *voiding phase* from our extensive and meticulously collected neuroimaging raw data available to us from our prior completed cohort. Aim 3 is a small, pilot feasibility study (n=8).

**Study duration:** Based on our experience, we anticipate that one year will allow appropriate time for data analysis for Aims 1 and 2. An additional (concurrent) 1-2 years will allow for appropriate patient recruitment, performance of the protocols, and data evaluation for Aim 3.

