## Description of interventions

**Subject Evaluations:** Each patient will undergo a detailed history and physical examination with the following assessments: Demographic Form, American Urological Association Symptom Score (AUASS), Neurogenic

Bladder Symptom Score (NBSS), MRI Safety Screening Questionnaire, Hospital Anxiety and Depression Scale, and Expanded Disability Status Scale. AUASS and NBSS both include questions regarding the voiding phase and are validated in neurogenic patients. Postvoid residual urine, urinalysis, urine culture, and pregnancy (if applicable) will be assessed prior to the MRI scan. A clinical UDS will be performed within 10 years prior to the neuroimaging scan. Consent will be signed during the first visit. High density Electromyography (EMG) will be performed at the beginning of the first and the last sessions of TRPMS treatment however this is an optional testing and patients can refuse to participate in the EMG testing. Patients from Group 1 who participate in the TRPMS will undergo a repeat fMRI scanning following the completion of the therapy. In addition their symptoms will be assessed with repeat UDS and validated questionnaires.

After their post TRPMS Intervention Fmri visit, subjects will return to the clinic to complete 4 months (+/- 1 month) and 12 months (+/-1 month) follow up visits. At these follow-up visits, they will completing validated questionnaires, uroflow testing and PVR scan.

**Simultaneous UDS/fMRI:** Double lumen 7 French MRI-compatible catheters are placed in the bladder and rectum. Either 3T or 7 T full body MRI scanner with standard 12 channel head coil is used. Instructions to communicate using right hand signals representing “strong desire to void” and “voiding” are given. In order to keep our noise-to-signal ratio low, all stimulators including any extra visual stimuli and the UDS machine are removed from the MRI room. Filling and voiding cycles are repeated up to 4 times in each patient. If the patient is unable to void, then the bladder will be drained passively.

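### Aim 2 is worded as showing that tract damage independently predicts voiding dysfunction, but the planned work can show only an association

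*Combined protocol and SAP*

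**What the plan says.** In the combined protocol and SAP, under Objectives/Specific Aims/Hypotheses, the heading of Aim 2 asserts that tract damage in female MS patients "provides an independent predictive measure for VD". Two tasks follow: "Measure fractional anisotropy (FA) and mean diffusivity (MD) of the ATR and SLF in Groups 1a, 1b, and 2" and "Assess whether damage to SLF or ATR are associated with voiding dysfunction in our patient population". The matching entry under Secondary Endpoints is "FA and MD of ATR and SLF white matter tracts in Groups 1 and 2".

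Experimental Plan and Feasibility says that "Aims 1 and 2 are retrospective analysis of the" voiding phase, using "neuroimaging raw data available to us from our prior completed cohort". Data Collection and Statistical Analysis describes how the diffusion images are acquired and the tracts extracted, and ends with "This software also enables calculating FA and MD values for the segmented WMTs". No statistical method for those values follows. On timing, Description of Interventions states: "A clinical UDS will be performed within 10 years prior to the neuroimaging scan".

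**The concern.** The heading makes two claims that the tasks beneath it do not test. 'Independent' means that the tract effect remains after other explanations are accounted for, but the plan does not say independent of what. 'Predictive' means either that tract damage comes before VD or that it classifies new patients with measured accuracy. The plan describes neither.

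The main rival explanation is overall disease burden. The protocol justifies Aim 2 by noting that MS lesions mainly affect white matter. A patient with more widespread damage may have lower FA in almost any tract and also be more likely to have VD. A difference in the anterior thalamic radiation (ATR) or superior longitudinal fasciculus (SLF) could then reflect severity alone, yet under the present heading it would be reported as tract-specific and prognostic.

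**Working it through.** **1. Claim against plan.**

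| Needed for the claim | What the plan contains |
|---|---|
| Independence: named covariates or a reference measure | None stated for FA or MD |
| Prediction over time: tract measure first, VD later | Completed cohort, no follow-up for later VD; clinical urodynamics (UDS) up to 10 years before the scan |
| Prediction as accuracy: discrimination, validation | None stated |
| A DTI test, alpha and multiplicity rule | None; the t-test or non-parametric test is for voxel activation, and the two-sided FDR-corrected 0.05 is for functional connectivity |

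**2. Group size.** The Power Analysis starts from 12 subjects and allows 10% exclusions: 12/0.9 = 13.3, or 12 × 1.1 = 13.2. Either rounds up to 14; the plan states 13 per group, N = 26, which is close enough. That calculation concerns single-voxel fMRI activation, not DTI. I use 13 per group below.

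**3. How often severity alone gives a significant result.** Assumptions, none of them from the documents:
- Severity S is standard normal.
- FA (sign reversed, so higher means worse) = rS + √(1 − r²)·e₁.
- VD liability = rS + √(1 − r²)·e₂, with no direct link between the two.
- VD is liability above its median, with 13 patients drawn from each side.
- The test is a two-sided t-test at 0.05 with 24 df.

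FA and liability then correlate r². Mean FA in the upper half is m = r²·√(2/π) = 0.798r², so the standardised group difference is d = 2m/√(1 − m²). At r = 0.7, m = 0.798 × 0.49 = 0.391 and d = 0.782/√(1 − 0.153) = 0.85.

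| r | d | Significant, from d | Significant, simulated | Simulated, adjusted, covariate 70% reliable |
|---|---|---|---|---|
| 0.2 | 0.06 | 5.3% | 5% | about 5% |
| 0.3 | 0.14 | 6.4% | 6% | about 5% |
| 0.4 | 0.26 | 9.7% | 9–10% | 6% |
| 0.5 | 0.41 | 16.9% | 16–17% | 6–7% |
| 0.6 | 0.60 | 31.2% | 31–32% | 8% |
| 0.7 | 0.85 | 54.7% | 54–56% | 11–13% |

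Ranges show the spread over repeat simulations of at least 4,000 trials per scenario. With perfectly measured severity as covariate, the rate is about 5% throughout.

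**4. What 26 patients can support.** Unadjusted, 80% power needs a standardised difference of about 1.15 at 13 per group; at 0.8 the power is 50%. Regressing a tract measure on group plus one covariate leaves 26 − 3 = 23 residual df instead of 24. A logistic prediction model with one tract measure and three covariates would have 13/4 = 3.25 VD cases per term, too few for a credible predictive claim.

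The check takes Groups 1 and 2 as disjoint. Their stated residual limits (at least 20% and below 40% of capacity) overlap. That is a separate matter, but it has to be reconciled before any comparison of these groups.

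**The case against.** The strongest reply is that the phrase is only a heading in a section that also states hypotheses. The task beneath it already speaks of association, and the endpoint is secondary and makes no predictive claim. This limits the harm but does not remove the contradiction: the heading states the conclusion the aim is meant to support.

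A reader might also infer four stronger points that the documents do not support:
- *That the plan prescribes an unadjusted t-test for FA and MD.* It prescribes nothing for them. The calculation above shows what a plain comparison would do, not what the plan commits to.
- *That EDSS, age and whole-brain diffusion measures are in hand and ignored.* EDSS and a demographic form are listed in the future tense for patients to be evaluated. The variables held for the earlier cohort are not listed, and only selected tracts are described as extracted.
- *That tract damage and VD were measured at the same time.* Groups rest on clinical and UDS data. The UDS may be up to 10 years older than the scan, while residual urine is assessed shortly before it. Timing is mixed, and it is not stated whether that window applied to the earlier cohort. Prediction fails because no later VD is observed, not because measurement was simultaneous.
- *That a positive result would probably be spurious.* At r = 0.2–0.3 the error rate is close to nominal. Restriction to stable disease and EDSS up to 6.5, if it applied to the earlier cohort, narrows the severity range and would tend to weaken confounding.

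It is also fair to object that adjustment is imperfect. A covariate sharing the tract's disease process can remove true signal, and an unreliable one leaves confounding behind. Both points stand, and they are why the adjusted result cannot earn the word 'independent'.

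**Conclusion.** The concern holds as a mismatch between claim and plan. Association is the most that Aim 2 can deliver; neither independence nor prediction would follow from a positive result. This conclusion needs no simulation.

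The size of possible confounding depends on an unknown r. It is negligible at 0.2–0.3, roughly two to three times nominal at 0.4–0.5, and large at 0.6–0.7 (31% to 56%). These figures assume equal correlations for FA and VD, no direct link and a plain two-group test. One well-measured severity covariate largely removes the excess. At 70% reliability up to about 12–13% remains at r = 0.7. The aim is secondary and the correction is cheap, so it should be made but is not critical to the trial.

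**What to change.** 1. In the heading of Aim 2, replace the claim with *is associated with VD*, in line with the task beneath it.
2. State the DTI analysis before it is run: for each of the four tract measures (FA and MD of ATR and SLF), the Group 1 v Group 2 difference with a 95% CI, unadjusted and adjusted for one severity covariate.
3. Name that covariate in advance, either EDSS or mean FA (for MD, mean MD) of the remaining white matter, after confirming it is available for the earlier cohort.
4. Label the adjusted estimates exploratory, and do not claim independence on them alone.

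The cost is a more modest claim, one degree of freedom (24 to 23) and possibly some true signal lost to the covariate. Interval width hardly changed in the simulated settings. In general, if the covariate explains a share R² of the group variance, the width is multiplied by 1/√(1 − R²), that is 1.12 at 20% and 1.29 at 40%, before any gain from lower residual variance. The Power Analysis says data analysis is still pending, so all of this can be specified without new data collection if the covariate exists.
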